Specific Aim #2: To assess whether subjects receiving the intervention will demonstrate fewer hospital readmissions at 24 weeks compared to control subjects in a randomized controlled trial.

Hypothesis 2: Subjects receiving the intervention will report fewer hospital readmissions at 24 weeks compared to control subjects.

III. Subject selection:

Inclusion criteria:

- English speaking, adults aged 18-75
- DSM-5 opioid use disorder, severe, actively using illicit opioids until the time of hospitalization
- Have a working telephone
- Can identify at least 2 individuals who can act as points of contact following discharge from the hospital
- Willing to engage in treatment (either a psychosocial treatment program AND/OR any medication treatment with methadone or buprenorphine)
- In SUD treatment for less than 6 months and/or not currently in treatment

Exclusion criteria:

- Liver function test >3x upper normal limit
- Pregnant
- Psychotic disorder, active suicidality or homicidality

- Condition likely to be terminal in 24 weeks such as cancer
- Unable to perform consent due to mental status

IV. Subject enrollment:

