analgesia. At the initial screen, all eligible English-speaking OUD patients will be offered a referral to methadone treatment and informed about the trial. Extended-release naltrexone, which requires that all opioids be stopped 7-10 days prior to initiation, will not be offered because the vast majority of patients screened will have received opioid analgesic during the hospitalization. As such, most potential patients would not be able to initiate naltrexone prior to discharge. Initiation of buprenorphine will be considered for patients who are medically stable enough to undergo induction, have an interest in initiating buprenorphine maintenance treatment, and have no medical or surgical contraindications. The full inclusion and exclusion criteria will then be applied.

V. Study procedures:

Randomization: After informed consent is given, participants will be randomized using a computerized random number generator with numbers in sealed envelopes in study binders.

Interventions:

Control group: Participants in the control arm will receive treatment-as-usual at our hospital. All participants will receive a thorough psychosocial evaluation to help with discharge planning. Following initiation of buprenorphine or methadone, the addiction social worker will provide the participant with the intake number for the BWH-affiliated buprenorphine programs, or contact information for relevant methadone programs. Patient preference due to geographic considerations will be taken into account when choosing the clinic to which participants are

Table 2: Components of the ISTOP intervention
In-hospital component (adapted from MISSION manual)

Session #1: (90 minutes with Recovery Coach)

- 1) Introduce recovery coach, and review overall intervention
- 2) Complete a psychosocial needs assessment
- 3) Create a provisional treatment plan based on identified service needs and prioritizing of goals.
- 4) Refer to BWH/BWFH-affiliated buprenorphine clinic
- 5) Use motivational interviewing to increase motivation for treatment
- 6) Review the following areas:
 - A. Monitoring and managing symptoms:
 - Review importance of buprenorphine adherence in managing cravings and preventing relapse.
 - Help identify cravings and warning signs of relapse
 - B. Patient education and self-management:
 - Educate about addiction and role of buprenorphine.
 - Review relapse prevention skills to cope with high-risk situations, cravings, and negative emotions

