Sample size/power analysis: In a study of a care management intervention for patients with substance use disorder in primary care, individuals receiving the intervention were more likely to remain in treatment at 24 weeks (40% vs 10%).⁵² While this study is entirely community based, no other comparable studies have been conducted with OUD patients on buprenorphine. Based on this effect size, we plan to screen 145 participants, assuming a 60% attrition due to screening failure, allowing for a sample size of 58 available for analysis, evenly divided between the control and intervention arm. This will yield a statistical power of 0.8 and 95% confidence level to detect differences in proportions of participants who remain in treatment at 24 weeks, as confirmed by the BWH-affiliated clinic. The study will not be powered to detect smaller effect sizes, but will be helpful in providing important information about effect sizes to adequately power future studies.

Specific Aim #1: The hypothesis that participants receiving the intervention will be more likely to remain in buprenorphine treatment at 24 weeks will be tested using logistic regression, treating the endpoint as a categorical variable. Treatment retention data will be obtained directly from the BWH/BWFH affiliated buprenorphine clinics. The hypothesis that participants receiving the intervention will report fewer days of illicit opioid use at 24 weeks will be tested using mixed effects ANOVA modeling, treating the endpoint as a continuous variable. ANCOVA will be used to adjust for relevant covariates, including age, sex, ethnicity/race, and baseline illicit opioid use. Illicit opioid use will be determined from the TLFB and urine toxicology results.

Specific Aim #2: The hypothesis that participants receiving the intervention will be less likely to be readmitted at 24 weeks will be tested using logistic regression, treating the endpoint as a categorical variable. Readmission data will be obtained from the ASI and GAIN service utilization items.⁸⁰ Results will be adjusted for relevant covariates, including demographic variables and baseline clinical variables. While 30-day readmission rate is an important metric for hospitals, the readmission rate at 24 weeks may better evaluate the impact of the proposed intervention.

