Missing data: Extensive efforts will be made to avoid missing data by vigorous outreach. Missing data on treatment continuation or retention will be imputed as treatment discontinuation (i.e. participant did not continue or remain in treatment). Missing urine toxicology samples will be treated as positive for illicit opioid use. Data on possible reasons for missing observations will be collected so that missing data mechanism may be appropriately modeled statistically. Using methods to manage missing data, results will be compared to the original dataset to identify any discrepancies and verify conclusions.

VII. Risks and discomforts

The well being of the study participants is of utmost importance. The in-depth screening procedure has been designed to ensure that individuals with any underlying medical or psychiatric illness are identified that may place them at greater risk for experiencing adverse effects during the study. The study procedures are designed to be minimally invasive and associated with minimal risk. Alternative procedures with lower risk are not available. Nevertheless, the protocol raises several areas of concerns: confidentiality, emotional distress, suicidal ideation, buprenorphine medication, intoxication, and overdose.

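### The randomization text gives no allocation ratio, blocks or strata, so neither equal arms nor balance on treatment type is assured; treatment type matters more than arm size

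*Combined protocol and SAP*

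**What the plan says.** The whole allocation method is one sentence in Section V (Randomization): after consent, "participants will be randomized using a computerized random number generator with numbers in sealed envelopes in study binders". Nothing states the allocation ratio, whether the list is blocked, any stratification factor, or who prepares it. Section IV adds that under remote enrollment the research assistant who introduces the study and holds the consent discussion then also randomizes the participant.

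Section VI (Sample size/power analysis), repeated in Section IX item 3, relies on "allowing for a sample size of 58 available for analysis, evenly divided between the control and intervention arm".

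On treatment type the sections differ:

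- Section III admits patients who are "Willing to engage in treatment (either a psychosocial treatment program AND/OR any medication treatment with methadone or buprenorphine"), and Section IV describes the population in the same terms.
- Section IV offers a methadone referral at the initial screen. Section V describes discharge planning in both arms after starting either buprenorphine or methadone.
- Section VII (Buprenorphine medication safety) says every subject will have started buprenorphine before randomization.
- Section VI (Specific Aim #1) takes retention data from the affiliated buprenorphine clinics. The covariates it names are age, sex, ethnicity/race and baseline illicit opioid use; treatment type is not among them.
- Section VI (Missing data): "Missing data on treatment continuation or retention will be imputed as treatment discontinuation".

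**The concern.** Two things the analysis depends on are left unspecified.

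The first is arm size. The power statement is written for two arms of 29, and nothing in the randomization text secures them.

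The second is treatment type. If a participant attends a methadone or psychosocial program, the affiliated buprenorphine clinics may hold no retention record, and the missing-data rule would then count that participant as having discontinued. Type at entry could thus largely decide who can be counted as retained. In a trial of 58, a chance excess of such participants in one arm would move the observed retention difference for reasons unrelated to the recovery coach, and the planned model does not name the factor.

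**Working it through.** **Inputs.** From Section VI: 58 analysed, 40% versus 10% retained, power 0.80, 95% confidence (taken as two-sided alpha 0.05, since sidedness is not stated). The share of participants not on buprenorphine is not given, so 10% to 50% is assumed.

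**Reproducing the plan's figure.** With unpooled variance, n per arm = (1.960 + 0.842)² × (0.4×0.6 + 0.1×0.9) / 0.3² = 28.8. That rounds to 29 per arm, 58 in total, power 0.803. The stated size reproduces. Screening is consistent too: 145 × 0.4 = 58.

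**Arm size if the list is unrestricted.** The intervention arm is Binomial(58, 0.5), with SD √58/2 = 3.8. P(29/29) = 0.104, P(difference of 8 or more) = 0.358, P(difference of 10 or more) = 0.237.

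**Power at 40% versus 10%.** Wald and score values are exact enumerations; Wald is the log odds ratio test, with tables containing a zero cell counted as non-significant.

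| Intervention/control | Wald | Score | Unpooled formula |
|---|---|---|---|
| 29/29 | 0.714 | 0.778 | 0.803 |
| 34/24 | 0.639 | 0.749 | 0.823 |
| 24/34 | 0.708 | 0.820 | 0.760 |
| averaged over all splits | 0.698 | 0.780 | 0.796 |

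The average change is 0.714 − 0.698 = 0.016 lost (Wald), 0.002 gained (score) and 0.803 − 0.796 = 0.007 lost (unpooled). The 34/24 and 24/34 splits are equally likely, and which is worse depends on the test. The differences between columns at 29/29 come from the choice of test, not from randomization.

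**With blocks of 4 (assumed), unstratified.** 58 = 14×4 + 2, so the worst split is 30/28, with unpooled power 0.796 to 0.809. With two strata each list can end mid-block by 2, so the worst is 31/27.

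**Balance on treatment type, 29 per arm, arms drawn independently.** SD of the difference in share = √(m(1−m)×2/29). At m = 0.3 this is √(0.21×2/29) = 0.120. The chance of a difference of 20 points or more is about 2% (m = 0.1), 7% (0.2), 11% (0.3) and 15% (0.5). Fixing the trial-wide number of such participants at 6, 12, 17 or 29 instead gives 2%, 10%, 8% and 11%.

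**What a 20-point imbalance could do.** Take m = 0.3 and the extreme case that no such participant can be counted as retained. Keeping 40% and 10% overall, retention among buprenorphine participants is 0.40/0.7 = 57.1% and 0.10/0.7 = 14.3%. With shares of 20% (intervention) and 40% (control), the expected difference is 57.1×0.8 − 14.3×0.6 = 37.1 points. With the shares reversed it is 57.1×0.6 − 14.3×0.8 = 22.9 points. The planned difference is 30, so the shift is about 7 points either way.

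**Value of adjusting for type.** In the same extreme case, simulation of a score test stratified by type raises power from 0.77–0.78 to 0.78–0.80 at a 10% share and from 0.78 to 0.83–0.84 at 30%, with type I error near 5%. The ranges reflect simulation details. Nearly all the gain comes from using type in the analysis. With arms of 29 each, adjusted power is about 0.80 and 0.84 whether or not allocation was stratified.

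**The case against.** The strongest reply is that the text is silent rather than wrong. A random number generator can produce a blocked list or a random ordering of 29 and 29 assignments, and envelopes prepared in advance fit either. A reader might infer that the trial uses simple randomization; the documents do not say so. This stands, and the point is confined to what is not specified.

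Second, a reader might infer that the sample size fails because 29/29 is unlikely. It does not. The average power loss is at most about 0.016, nil for the score test, and some unequal splits raise power.

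Third, Section VII would leave little treatment type to balance at randomization. That also stands: the treatment-type half is conditional on how the conflict with Sections III, IV and V is resolved. Even outside Section VII, the documents do not establish that type is settled before allocation, because starting buprenorphine or methadone is described within the arms. Only intended type could serve as a stratum.

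Fourth, unrestricted randomization is valid, chance imbalance does not bias the test, and unpredictability has value where the person recruiting may also randomize. This is a fair argument for varying, concealed block sizes. It does not excuse leaving the method unstated.

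Last, the importance of type derives from where retention data come from. If retention in any program could be verified, the case for stratifying would weaken greatly. Stratifying does not cure that separate issue.

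**Conclusion.** The point holds as a gap in specification with a cheap remedy. Equal arms are assumed but not assured, and the consequence for power is minor; N = 58 stands. Treatment type is the more important part. If mixed types are enrolled and retention is seen only through affiliated buprenorphine clinics, type may strongly predict the endpoint. The arms would then differ by 20 points or more in about 2% to 15% of trials, and at a 30% share a 20-point difference could move the expected retention difference by about 7 points.

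Those figures rest on an assumed non-buprenorphine share, and the 7 points also on none of those participants being countable as retained. The documents do not support saying that the primary result will be biased or that imbalance will occur. If every subject starts buprenorphine before randomization, this half largely falls away and only the missing allocation details remain.

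**What to change.** 1. Reconcile Section VII (all subjects on buprenorphine before randomization) with Sections III, IV and V (methadone or psychosocial treatment allowed). Which is intended is for the investigators to settle.
2. State 1:1 allocation by permuted blocks of randomly varying size. Have the list and envelopes prepared by someone outside recruitment, with block sizes concealed from the research assistant who enrolls and may randomize.
3. If mixed treatment types remain, record intended type (buprenorphine or other) before the envelope is opened. Make it the only stratification factor, given 58 participants, and include it in the retention model. If no participant in the other stratum is retained, ordinary logistic regression has no finite estimate for that term, so name a stratified score test or penalized logistic regression as the fallback.

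The cost is a new list and a few lines in Sections V and VI, with no extra participants. The downside is slightly more predictable allocation in an open-label trial, which varying block sizes limit.

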The proposed project addresses these unmet needs by testing a novel intervention to improve the treatment of OUD patients hospitalized for medical reasons. The intervention will

combine 1) medication-assisted treatment with buprenorphine initiated in the hospital, 2) care management to address domains known to improve transitions of care (monitoring and managing symptoms, encouraging self-management skills, and enlisting community and social supports⁴⁰⁻⁴³), and 3) recovery coaches to assist the patient in the community after discharge from the hospital. Previous studies lacked one or more of these components, or were not focused on OUD patients. While the use of buprenorphine has been studied with hospitalized patients, previous studies did not provide longitudinal support in the community following discharge.^{34,36} Previous studies on transitions of care have not specifically targeted hospitalized OUD patients, even though drug use is a well-known risk factor for readmissions.⁷ Care management has been frequently utilized to manage complex patients, but no prior studies have targeted hospitalized OUD patients being discharged into the community. Finally, recovery coaches have also not been studied to improve treatment retention of OUD patients treated with buprenorphine⁵⁹. In this study, the trainings and responsibilities of the recovery coach and care management will be merged into one role. Further, this study brings these promising elements together into one novel model. If successful, this model could prove useful for engaging hospitalized out-of-treatment OUD patients.

II. Aims:

Our hypothesis is that the recovery coach intervention will be associated with greater success not only in remaining in treatment, but also in reducing the likelihood of hospital readmissions.

Specific Aim #1: To assess whether subjects randomized to the recovery coach intervention will demonstrate greater retention in treatment and better opioid use outcomes at 24 weeks compared to control subjects in a randomized controlled trial.

Hypothesis 1a: Subjects receiving the intervention will be more likely to remain in treatment at 24 weeks, as compared to control subjects.

Hypothesis 1b: Subjects receiving the intervention will report fewer days of illicit opioid use in the prior 30 days at 24 weeks, as compared to control subjects.

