- b. Measurement and reporting of participant adherence to treatment protocol: Data on adherence to the treatment protocol will be collected weekly by research staff and reviewed quarterly by the PI. Fidelity to the treatment manual will be reviewed by the candidate each week with the recovery coaches.

3. Justification of sample size: In a study of a care management intervention for patients with substance use disorder in primary care, individuals receiving the intervention were more likely to remain in treatment at 24 weeks (40% vs 10%). While this study is entirely community based, no other comparable studies have been conducted with OUD patients on buprenorphine. Based on this effect size, we plan to screen 145 participants, assuming a 60% attrition due to screening failure, allowing for a sample size of 58 available for analysis, evenly divided between the control and intervention arm. This will yield a statistical power of 0.8 and 95% confidence level to detect differences in proportions of participants who remain in treatment at 24 weeks, as confirmed by the BWH-affiliated clinic. The study will not be powered to detect smaller effect sizes, but will be helpful in providing important information about effect sizes to adequately power future studies.

4. **Stopping rules:** This study will be stopped prior to its completion if: (1) the intervention is associated with adverse effects that call into question the safety of the intervention; (2) difficulty in study recruitment or retention will significantly impact the ability to evaluate the study endpoints; (3) any new information becomes available during the trial that necessitates stopping the trial; or (4) other situations occur that might warrant stopping the trial
5. **Designation of an independent monitor:** To minimize any conflicts of interest, a physician from Brigham and Women's Hospital familiar with clinical research who is not a collaborator or investigator on the proposed project, nor a close colleague, will serve as an independent individual to monitor the data and safety.

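### Does the stated power of 0.8 fail because Aim 1 does not say which logistic regression test it will use?

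*Combined protocol and SAP*

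**What the plan says.** Section VI, under the sample size heading, takes 24-week retention of 40% against 10% from a primary-care study of care management. It plans to screen 145 people, "allowing for a sample size of 58 available for analysis, evenly divided between the control and intervention arm", and continues: "This will yield a statistical power of 0.8 and 95% confidence level to detect differences in proportions of participants who remain in treatment". Section IX.3 repeats the text. Neither place gives a formula or says whether the test is one- or two-sided.

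The Aim 1 analysis says that the hypothesis of participants being "more likely to remain in buprenorphine treatment at 24 weeks will be tested using logistic regression, treating the endpoint as a categorical variable". It does not say whether the arm coefficient is judged by a Wald, score, likelihood-ratio or penalized test. The paragraph then moves to days of illicit opioid use, analysed by mixed-effects ANOVA, and only after that says "ANCOVA will be used to adjust for relevant covariates, including age, sex, ethnicity/race, and baseline illicit opioid use". Hypothesis 1a in section II is directional: "Subjects receiving the intervention will be more likely to remain in treatment at 24 weeks, as compared to control subjects".

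Under the missing data heading in section VI, unknown retention counts as discontinuation, so every randomized participant has an outcome.

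**The concern.** The power sentence speaks of a difference in proportions, while the analysis is a logistic regression. In large samples the distinction hardly matters. With 29 per arm and about three retained controls expected (29 × 0.10 = 2.9), Wald, score and likelihood-ratio tests of the same model can fall on different sides of 0.05. There is also a real chance that no control is retained. The ordinary odds ratio is then not finite and a Wald test cannot reject.

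Two things would be at stake. The real power could be below 0.8. And the Aim 1 verdict could, in some trials, depend on a software default or on a choice made after the data are seen.

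**Working it through.** **Inputs.** Retention 0.40 and 0.10, and 58 analysed at 1:1, so 29 per arm (section VI, sample size). Alpha 0.05, read from the 95% confidence level. Screening: 145 × (1 − 0.60) = 58. Two-sided testing and an arm-only model are assumptions, examined below.

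**1. The plan's own figure.** Unpooled normal approximation:

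- n per arm = (1.960 + 0.8416)² × (0.4×0.6 + 0.1×0.9) / 0.30² = 7.849 × 0.33 / 0.09 = 28.78, rounded up to 29, total 58.
- Power at 29 = Φ(0.30 / √(0.33/29) − 1.960) = 0.803.
- Exact power of that z-test, summed over all 30 × 30 possible tables, is 0.808, with size 0.054 when both arms are at 10%.

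Both the 0.8 and the 58 reproduce. Other formulas give somewhat different values (arcsine 0.789, pooled variance 0.765), but the unpooled one yields exactly the planned number.

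**2. Sidedness.** A one-sided 0.05 test would need (1.645 + 0.8416)² × 0.33 / 0.09 = 22.67, so 23 per arm. The planned 29 fits the two-sided reading.

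**3. Exact power of the logistic tests.** Arm-only model, 29 per arm, two-sided 0.05, all 900 tables weighted by Binomial(29, 0.40) × Binomial(29, 0.10):

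| Test | Power at 40%/10% | Size at 10%/10% | Size at 25%/25% | Maximum size |
|---|---|---|---|---|
| Wald, empty-cell tables counted as non-significant | 0.714 | 0.007 | 0.043 | 0.048 |
| Wald, score test in empty-cell tables | 0.761 | 0.038 | 0.044 | 0.048 |
| Score | 0.778 | 0.053 | 0.048 | 0.055 |
| Firth penalized likelihood ratio | 0.778 | 0.053 | 0.048 | 0.055 |
| Likelihood ratio | 0.806 | 0.076 | 0.059 | 0.089 |

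Firth and score make the same decision in all 900 tables.

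**4. Where the low Wald figure comes from.** The chance of no retained controls is 0.9²⁹ = 0.047. Nearly all those tables are significant by the score test, and 0.714 + 0.047 = 0.761. So the step from 0.71 to 0.76 is entirely the treatment of tables in which the fitted odds ratio is visibly unusable.

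**5. How often the choice changes the verdict.** At 40%/10%:

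- Score against Wald with fallback: 1.7% of trials.
- Score against likelihood ratio: 2.8%.
- Plain Wald against likelihood ratio: 9.2%, of which 4.7 points are empty-cell tables and 4.5 points are ordinary tables.

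The ordinary tables are essentially four (intervention/control retained): 9/3 (2.3%), 8/2 (1.5%), 13/6 (0.5%) and 6/1 (0.2%). For 9/3 the p-values are 0.048 (likelihood ratio), 0.052 (score), 0.056 (Firth) and 0.062 (Wald). All four are borderline and would be read much alike.

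**6. Scale against the inputs.** Score-test power is 0.70 at 40%/12%, 0.73 at 38%/10% and 0.85 at 40%/8%. A shift of two percentage points in one assumed rate moves power by 5 to 8 points, more than the choice among the sensible tests.

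**7. Covariates.** The adjustment sentence follows the analysis of opioid-use days and names ANCOVA, which is a method for a continuous outcome. Aim 2 states separately that its logistic results are adjusted; the Aim 1 retention sentence does not. The natural reading is an arm-only retention model. If covariates were added, the effect on power could go either way. In simulation with four covariates (two normal, two binary), adjusted Firth power is 0.74 when none has any effect. When the two normal ones are prognostic, it is 0.78 at a log-odds of 0.5 per standard deviation, 0.80 at 0.8 and 0.85 at 1.2. The documents do not say how prognostic the covariates are, so no single figure can be attached to an adjusted model.

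**The case for a change.** The best case for a change is that the primary decision rule should be complete before data are seen, and here it is not. Among the logistic tests only the likelihood ratio reaches 0.8, and it does so with size above 0.05 when retention is low. The empty-cell risk may also exceed 4.7%. Missing retention counts as discontinuation, and the background section cites 3.0% six-month retention in one control arm. At a 5% control rate the chance of no retained controls is 0.95²⁹ = 23%; at 3% it is 0.97²⁹ = 41%. A few sentences naming a Firth test would settle the matter at no cost in enrolment.

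Part of this stands. The test and its sidedness are not stated, and naming them would be tidy. The rest carries less weight. The 3.0% arm received detoxification alone, whereas controls here are referred on to continuing treatment, so it is a weak guide. When no control is retained, any analyst sees that the ordinary estimate has failed, and a score test on the same table still gives a valid answer. Firth adds nothing to the decision itself, since it agrees with the score test in every table; its gain is a finite odds ratio in the empty-cell tables. Requiring it, or making any adjusted model supportive only, would be a design preference and not the repair of an error.

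**Conclusion.** No change is needed. The stated power is right for the comparison of proportions it describes (0.803 approximate, 0.808 exact), and the sample size follows from it. What is missing is the name of the logistic test, a detail that analysts routinely supply. The sensible choices give power between 0.76 and 0.81, and two of them, score and Wald with a fallback, disagree in 1.7% of trials. The likelihood-ratio test's size of 0.076 applies when both arms retain 10%; it is 0.059 at 25% and at most 0.089. None of this affects the validity of the trial, and the plan already says that the study is not powered for smaller effects and is meant to inform later ones.

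The conclusion assumes a two-sided 0.05 test, which the planned 58 supports; an arm-only retention model, which is the natural reading of Aim 1; and the plan's own rates of 40% and 10%.
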